10. MEASUREMENTS

Primary Outcome Measure

Definition: Overall response defined as either complete response or partial response assessed using RECIST v1.1 criteria. This measure will be reported as a number without dispersion.

- Title: overall response
- Time Frame: 8 (+/-4) weeks from start of treatment.
- Safety Issue: No

10.1 Primary outcome measure

The primary endpoint will be overall response assessed 8 (+/-4) weeks from start of treatment using RECIST v1.1 criteria (please see details below for how this will be measured and defined).

10.1.1 Relevant Subset

Overall response rate will be reported for all patients who receive at least 1 dose of the study agent. Subjects receiving less than that or no study agent will be determined as inevaluable for the primary outcome though their data will still be collected for safety and survival purposes.

10.1.2 Measurement Definition- Antitumor Effect- Solid Tumors

Response and progression will be evaluated in this study using the international criteria proposed by the Response Evaluation Criteria in Solid Tumors (RECIST) Committee [JNCI 92(3):205-216, 2000]. Changes in only the largest diameter (unidimensional measurement) of the tumor lesions are used in the RECIST v1.1 criteria.

Definitions

Evaluable for toxicity. All subjects will be evaluable for toxicity from the time of their first treatment with study drug.

Evaluable for objective response. Only those subjects who have measurable disease present at baseline, have received at least one dose of therapy, and have had their disease re-evaluated will be considered evaluable for response. These subjects will have their response classified according to the definitions stated below. (Note: Subjects who exhibit objective disease progression prior to the end of cycle 1 will also be considered evaluable).

Disease Parameters

Measurable disease. Measurable lesions are defined as those that can be accurately measured in at least one dimension (longest diameter to be recorded) as ≥ 20 mm with conventional techniques (CT, MRI, x-ray) or as ≥ 10 mm with spiral CT scan. All tumor measurements must be recorded in millimeters (or decimal fractions of centimeters).

Note: Previously irradiated lesions are non-measurable except in cases of documented progression of the lesion since the completion of radiation therapy.

Non-measurable disease. All other lesions (or sites of disease), including small lesions (longest diameter <20 mm with conventional techniques or <10 mm using spiral CT scan), are considered non-measurable disease. Bone lesions, leptomeningeal disease, ascites, pleural/pericardial effusions, lymphangitis cutis/pulmonis, inflammatory breast disease, abdominal masses (not followed by CT or MRI), and cystic lesions are all non-measurable.

Target lesions. All measurable lesions up to a maximum of 3 lesions per organ and 6 lesions in total, representative of all involved organs, should be identified as **target lesions** and recorded and measured at baseline. Target lesions should be selected on the basis of their size (lesions with the longest diameter) and their suitability for accurate repeated measurements (either by imaging techniques or clinically). A sum of the longest diameter (LD) for all target lesions will

be calculated and reported as the baseline sum LD. The baseline sum LD will be used as reference by which to characterize the objective tumor response.

Non-target lesions. All other lesions (or sites of disease) including any measurable lesions over and above the 6 target lesions should be identified as **non-target lesions** and should also be recorded at baseline. Measurements of these lesions are not required, but the presence or absence of each should be noted throughout follow-up.

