9.1.1.11 Pregnancy test (for females of child bearing potential)

At screening visit, serum pregnancy test will be performed. Following the screening assessment, urine pregnancy tests should be performed. Pregnancy test must be performed according to the date windows listed under schedule of assessments.

9.1.1.12 *Tumor assessment*

To be performed using radiographic imaging according to Section 9.1.4.1.

9.1.1.13 *Information to be collected on screening failures*

A patient who signs an informed consent but fails to satisfy all eligibility criteria for any reason will be considered a screen failure. The demographic information, informed consent, and documentation supporting the reason for screenfail will be completed for Screen Failure patients. No other data will be entered into the clinical database for patients who are screen failures, unless the patient experienced a Serious Adverse Event during the Screening Phase (see SAE Section 7.4 reporting details).

9.1.1.14 *Replacement policy*

If an eligible patient is unable to start therapy with study treatment, they may be replaced with another eligible patient if they have not received any study drug.

Apart from the above, patients will not be replaced on this study.

9.1.2 *Treatment period*

Following completion of screening procedures and verifying patient eligibility, the patient will be approved for treatment per protocol.

The study treatment phase begins on Cycle 1, Day 1 with the first administration of abemaciclib and will continue to receive treatment until disease progression by RECIST, unacceptable toxicity, withdrawal of consent, or discontinuation of the trial for any other reason whichever occurs first. Patients who have RECIST-defined PD as assessed by the investigator but who, in the opinion of the investigator, have evidence of continued clinical benefit from abemaciclib may continue to receive the study medication upon approval by the principal investigator. In such cases, these patients must continue to be followed for safety and efficacy assessments as per the schedule of assessments. Patients will be assessed as per visit schedule in Table 9-1.

9.1.3 *End of treatment visit including study completion and premature withdrawal*

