9.1.4 Assessment types

9.1.4.1 Efficacy assessments

Efficacy evaluations will be via revised RECIST 1.1 criteria on imaging performed at the conclusion of every 2 cycles. Target lesions will be identified prior to initiation of therapy on imaging and will be followed on subsequent imaging.

Physical exam findings of progressive disease will be considered as sufficient for documented progression if the record records biopsy proven tumor measurements in 2 dimensions and shows an increase in both dimensions of 20%.

Imaging exams will be according to standard of care guidelines to areas of known/suspected disease. These will include CT of the neck, chest, abdomen and pelvis as well as MRI of the brain. Other tests may be clinically indicated, these will be ordered according to disease and patient specific guidelines. Imaging of the brain will be required at baseline by CT or MRI per standard of care for Anaplastic Thyroid Cancer.

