The best overall response is the best response recorded from the start of the treatment until disease progression/recurrence (taking as reference for progressive disease the smallest measurements recorded since the treatment started). The subject's best response assignment will depend on the achievement of both measurement and confirmation criteria.

Target Lesions	Non-Target Lesions	New Lesions	Overall Response	Best Response for this
----------------	--------------------	-------------	------------------	------------------------

				Category Also Requires:
CR	CR	No	CR	n/a
CR	Non-CR/Non-PD	No	PR	N/a
PR	Non-PD	No	PR	
SD	Non-PD	No	SD	Documented at least once ≥ 4 wks. from baseline
PD	Any	Yes or No	PD	no prior SD, PR or CR
Any	PD*	Yes or No	PD	
Any	Any	Yes	PD	
In exceptional circumstances, unequivocal progression in non-target lesions may be accepted as disease progression.				
Subjects with a global deterioration of health status requiring discontinuation of treatment without objective evidence of disease progression at that time should be reported as " symptomatic deterioration ". Every effort should be made to document the objective progression even after discontinuation of treatment.				

Note: If subjects respond to treatment and are able to have their disease resected, the patient's response will be assessed prior to the surgery.

Duration of Response

Duration of overall response: The duration of overall response is measured from the time measurement criteria are met for CR or PR (whichever is first recorded) until the first date that recurrent or progressive disease is objectively documented (taking as reference for progressive disease the smallest measurements recorded since the treatment started).

The duration of overall CR is measured from the time measurement criteria are first met for CR until the first date that recurrent disease is objectively documented.

Duration of stable disease: Stable disease is measured from the start of the treatment until the criteria for progression are met, taking as reference the smallest measurements recorded since the treatment started.

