12.4 Primary Analysis

12.4.1 Analysis Population

The Full Analysis Set (FAS) comprises all consented patients who receive at least one dose of abemaciclib.

The Safety Set includes all patients who received at least one dose of abemaciclib medication.

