12.4.2. Analysis Plan

Our primary analysis will be the calculation of the overall response rate, defined as the percentage of patients who have overall response in the full analysis set. The rate of overall response and its 95% confidence interval in the full analysis set will be estimated using exact binomial method.

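### Does the evaluability definition in Section 10.1.2 change the denominator of the primary response rate?

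*Combined protocol and SAP*

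**What the plan says.** Section 10.1 introduces the primary endpoint and refers the reader onward: "please see details below for how this will be measured and defined". Two subsections then deal with who counts.

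- Section 10.1.1 (Relevant Subset): "Overall response rate will be reported for all patients who receive at least 1 dose of the study agent". It treats as inevaluable for the primary outcome only those who received less than that.
- Section 10.1.2 (Measurement Definition): among dosed patients with measurable disease, only those who qualify by reassessment ("and have had their disease re-evaluated will be considered evaluable for response") have a response classified. A note adds patients with objective progression before the end of cycle 1.

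The statistical section sets the analysis. Section 12.4.1: "The Full Analysis Set (FAS) comprises all consented patients who receive at least one dose of abemaciclib". Section 12.4.2 gives the primary rate as a percentage, "defined as the percentage of patients who have overall response in the full analysis set", and computes the exact binomial 95% interval in that same set. Section 12.5.2 says that missing data are not imputed.

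The decision rule in Sections 12.2 and 12.6.2 is a count: stop if there are 0 responses in 9 patients, and declare success with 3 or more in 17. Section 9.1.1.14 allows replacement only of patients who never received study drug: "Apart from the above, patients will not be replaced on this study".

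**The concern.** Two neighbouring subsections use the language of evaluability for response and draw the line in different places. Because Section 10.1 points to the text below it for the definition of the endpoint, an analyst could take Section 10.1.2 as setting the denominator.

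The patients in dispute are dosed patients with no reassessment, and there may be several. Section 9.1.4.1 puts the first planned imaging after two 28-day cycles: "Efficacy evaluations will be via revised RECIST 1.1 criteria on imaging performed at the conclusion of every 2 cycles". Section 2.1.1 describes a disease with median survival of 3 to 4 months. Section 10.1.3 also creates a reporting category, for "Subjects with a global deterioration of health status requiring discontinuation of treatment without objective evidence of disease progression at that time", that has no row in its response table, and no sentence states that unassessed patients count as non-responders.

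Missing reassessment in this disease is unlikely to be random. Leaving these patients out would push the rate and its interval upward, and Section 12.7 plans a larger study to confirm that rate.

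**Working it through.** **1. Which text assigns the denominator.**

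| Place | Subject | Set named | Rate or interval named? |
|---|---|---|---|
| 10.1.1 | Relevant subset for the primary outcome | All with at least one dose | Rate |
| 10.1.2 | Whose response is classified | Measurable disease, dosed and reassessed (or early objective progression) | Neither |
| 12.4.1 | Full analysis set | All consented with at least one dose | Neither (defines the set) |
| 12.4.2 | Primary analysis | Full analysis set | Both |

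Every passage that names the rate or its interval assigns it to dosed patients. Section 10.1.2 names neither, and no analysis in Section 12 calls on it. The pointer in Section 10.1 leads first to Section 10.1.1, which gives the all-dosed set.

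**2. How an unassessed patient is scored under Section 12.4.2.** The rate is (patients with CR or PR) / (patients in the full analysis set). A dosed patient without reassessment belongs to the set and has no CR or PR, so adds 1 to the denominator and 0 to the numerator. The no-imputation rule supplies no response and removes nobody from the set.

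**3. The design figures.** Inputs from Section 12.6.2: null rate 0.05, alternative 0.30, 9 then 8 patients, stop at 0/9, success at 3 or more of 17. With X ~ Bin(9, p) and Y ~ Bin(8, p),

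P(success) = P(X=1)·P(Y≥2) + P(X=2)·P(Y≥1) + P(X≥3).

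- p = 0.05: 0.2985 × 0.0572 + 0.0629 × 0.3366 + 0.0084 = 0.0466.
- p = 0.30: 0.1557 × 0.7447 + 0.2668 × 0.9424 + 0.5372 = 0.9045.

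This agrees with the stated type I error of at most 0.05 and power of 0.9. The formula uses responder counts among accrued patients, and dosed patients cannot be replaced, so the denominator of the reported rate does not enter.

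**4. Size if Section 10.1.2 were applied instead.** The documents do not give the number of dosed patients never reassessed. Take d = 2 to 5 of 17 as an illustrative assumption. Responders have been reassessed by definition, so only the denominator changes and the rate is multiplied by 17/(17 − d). The exact limits are the 2.5% quantile of Beta(x, n − x + 1) and the 97.5% quantile of Beta(x + 1, n − x).

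| d | 3 responders (95% CI, %) | 5 responders (95% CI, %) | 17/(17 − d) |
|---|---|---|---|
| 0 | 3/17 = 17.6% (3.8 to 43.4) | 5/17 = 29.4% (10.3 to 56.0) | 1.00 |
| 2 | 3/15 = 20.0% (4.3 to 48.1) | 5/15 = 33.3% (11.8 to 61.6) | 1.13 |
| 5 | 3/12 = 25.0% (5.5 to 57.2) | 5/12 = 41.7% (15.2 to 72.3) | 1.42 |

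The d = 0 row is what Section 12.4.2 prescribes. The other rows require a departure from it.

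**The case for a change.** The strongest case for a change accepts that the full analysis set governs and turns on scoring. Section 10.1.2 provides a classification only for reassessed patients, Section 12.5.2 forbids imputation, and no sentence calls an unassessed patient a non-responder. An analyst could therefore treat the response as missing and drop the patient while still citing the full analysis set. Nor would such patients be rare. With exponential survival at medians of 4 and 3 months, 27% to 35% would die by day 56, or 4.6 to 5.9 of 17. At the 8.4-month median quoted in Section 2.1.3 for another treatment the figure is 14%, or 2.4 of 17. One or two sentences would settle the matter at no cost.

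Part of this stands. The documents do not say what the 10.1.2 set is for, and an explicit non-responder sentence is absent. The mortality figures are only indicative: they borrow medians from other populations and time origins, and this trial requires ECOG 0-1.

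The inference to a biased result does not stand. A percentage of patients in a named set has that set as its denominator, and dropping members of it would contradict Section 12.4.2. The disputed group is also smaller than it looks. A patient with symptomatic deterioration may already have been scanned, Section 10.1.3 asks for continued efforts to document progression after treatment stops, Section 9.1.4.1 accepts progression on physical examination under stated conditions, and Section 10.1.2 itself keeps early objective progression as evaluable. What remains is mainly patients who die or withdraw with no reassessment at all.

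**Conclusion.** The two definitions differ, but they do not compete for the primary analysis. Section 12.4.2, supported by Section 10.1.1, fixes the denominator as all dosed patients and leaves unassessed patients as non-responders by construction. Section 10.1.2 can be read as saying who receives a RECIST category.

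On that reading the reported rate and interval are sound as planned. The possible inflation, a factor of 1.13 to 1.42 for an assumed 2 to 5 unassessed patients of 17, arises only if the analyst departs from the written plan. The go/no-go decision, the type I error of 0.0466 and the power of 0.9045 are the same in either case, and no decision in the protocol rests on the confidence limits. Section 12.7 makes the larger study conditional on the response criterion, which is the responder count.

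This is a gap in wording that analysts would fill sensibly from the plan's own definition. Labelling the 10.1.2 set as supportive would be a courtesy to the reader and would change no result, so no change is called for.

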10.1.3 Measurement Methods

All measurements should be taken and recorded in metric notation using a ruler or calipers. All baseline evaluations should be performed as closely as possible to the beginning of treatment and never more than 30 days before the beginning of the treatment.

The same method of assessment and the same technique should be used to characterize each identified and reported lesion at baseline and during follow-up. Imaging-based evaluation is preferred to evaluation by clinical examination when both methods have been used to assess the antitumor effect of a treatment.

Conventional CT and MRI. These should be performed with cuts of 10 mm or less in slice thickness contiguously. Spiral CT should be performed using a 5 mm contiguous reconstruction algorithm.

CT scans of the neck, chest, abdomen and pelvis will be performed at baseline and every two cycles according to standard of care. Other imaging of these areas such as PET/MRI will be allowed if CT cannot be performed.

MRI of the brain will be performed at baseline and as clinically indicated. Wherever it can be safely given, radiographic contrast agents should be given for the imaging studies.

Response Criteria

(i)

Evaluation of Target Lesions

Complete Response (CR): Disappearance of all target lesions, determined by two separate observations conducted not less than 4 weeks apart. There can be no appearance of new lesions.

Partial Response (PR): At least a 30% decrease in the sum of the longest diameter (LD) of target

lesions, taking as reference the baseline sum LD. There can be no appearance of new lesions.

Progressive Disease (PD): At least a 20% increase in the sum of the LD of target lesions, taking as reference the smallest sum LD recorded since the treatment started, or the appearance of one or more new lesions.

Stable Disease (SD): Neither sufficient shrinkage to qualify for PR nor sufficient increase to qualify for PD, taking as reference the smallest sum LD since the treatment started.

(ii) Evaluation of Non-Target Lesions

Complete Response (CR): Disappearance of all non-target lesions and normalization of tumor marker level.

Incomplete Response/Stable Disease (SD): Persistence of one or more non-target lesion(s) and/or maintenance of tumor marker level above the normal limits.

Progressive Disease (PD): Appearance of one or more new lesions and/or unequivocal progression of existing non-target lesions

(iii) Evaluation of Best Overall Response

The best overall response is the best response recorded from the start of the treatment until disease progression/recurrence (taking as reference for progressive disease the smallest measurements recorded since the treatment started). The subject's best response assignment will depend on the achievement of both measurement and confirmation criteria.

Target Lesions	Non-Target Lesions	New Lesions	Overall Response	Best Response for this
----------------	--------------------	-------------	------------------	------------------------

				Category Also Requires:
CR	CR	No	CR	n/a
CR	Non-CR/Non-PD	No	PR	N/a
PR	Non-PD	No	PR	
SD	Non-PD	No	SD	Documented at least once ≥ 4 wks. from baseline
PD	Any	Yes or No	PD	no prior SD, PR or CR
Any	PD*	Yes or No	PD	
Any	Any	Yes	PD	
In exceptional circumstances, unequivocal progression in non-target lesions may be accepted as disease progression.				
Subjects with a global deterioration of health status requiring discontinuation of treatment without objective evidence of disease progression at that time should be reported as " symptomatic deterioration ". Every effort should be made to document the objective progression even after discontinuation of treatment.				

Note: If subjects respond to treatment and are able to have their disease resected, the patient's response will be assessed prior to the surgery.

Duration of Response

Duration of overall response: The duration of overall response is measured from the time measurement criteria are met for CR or PR (whichever is first recorded) until the first date that recurrent or progressive disease is objectively documented (taking as reference for progressive disease the smallest measurements recorded since the treatment started).

The duration of overall CR is measured from the time measurement criteria are first met for CR until the first date that recurrent disease is objectively documented.

Duration of stable disease: Stable disease is measured from the start of the treatment until the criteria for progression are met, taking as reference the smallest measurements recorded since the treatment started.

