12.5.2 Analysis Plan

Overall survival (OS) is defined as the time from start of treatment to death due to any cause. If a subject is not known to have died, then OS will be censored at the latest date the subject was known to be alive. The OS distribution will be estimated using the Kaplan-Meier method, and the Kaplan-Meier curves, medians and 95% confidence intervals of the medians will be presented.

Progression-free survival is defined as the time from start of treatment to date of progression or death due to any cause. If a subject is not known to have progressed or died, then PFS will be censored at the latest date the subject was known to be alive or disease-free. The PFS distribution will be estimated using the Kaplan-Meier method, and the Kaplan-Meier curves, medians and 95% confidence intervals of the medians will be presented.

In addition, we will estimate response duration using Kaplan-Meier methods.

For all safety analyses, the safety set will be used. Toxicities will be dichotomized as none versus any adverse event, or none and mild versus moderate to severe adverse event.

Summary tables for adverse events (AEs) will include only AEs that started or worsened during the on-treatment period, the treatment-emergent AEs, unless otherwise specified.

All safety data collected in the study will be listed regardless of the study period with data collected during the pre-treatment and post-treatment period flagged. The incidence of treatment-emergent adverse events (new or worsening from baseline) will be summarized by system organ class and or preferred term, severity (based on CTCAE grades), type of adverse event, relation to study treatment by the Principal Investigator and/or research team.

Deaths reportable as SAEs and non-fatal serious adverse events will be listed by patient and tabulated by type of adverse event.

Specific safety event categories (SEC) will be considered. Such categories consist of one or more well-defined safety events which are similar in nature and for which there is a specific clinical interest in connection with the study treatment(s).

For each specified category, number and percentage of patients with at least one event per category will be summarized.

Handling of missing values/censoring/discontinuations

All attempts will be made to ensure that the database contains complete information. No imputation will be applied for missing data.

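### Response duration has no stated rule for death or censoring; read literally, a responder who dies without documented progression is not an event

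*Combined protocol and SAP*

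**What the plan says.** Section 10.1.3 (Duration of Response) starts the clock when the criteria for complete or partial response are first met and runs it "until the first date that recurrent or progressive disease is objectively documented". The companion definition for complete response ends only at documented recurrence. Neither mentions death.

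Section 12.5.2 gives response duration one sentence: "In addition, we will estimate response duration using Kaplan-Meier methods". It states no event definition and no censoring date for it. In the same section OS and PFS each have both. For PFS, "Progression-free survival is defined as the time from start of treatment to date of progression or death due to any cause", and for patients without such an event, "PFS will be censored at the latest date the subject was known to be alive or disease-free". On missing data the section says: "No imputation will be applied for missing data".

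Two other places bear on how often the gap would matter. Section 9.1.4.1 bases efficacy on "imaging performed at the conclusion of every 2 cycles", which is every 56 days, and also accepts progression on physical examination if a biopsy-proven tumour has grown by 20% in both of two dimensions. The note to the best-response table in 10.1.3 gives a separate reporting category to "Subjects with a global deterioration of health status requiring discontinuation of treatment without objective evidence of disease progression at that time", and adds: "Every effort should be made to document the objective progression even after discontinuation of treatment".

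Section 10.2 lists OS, PFS and safety as secondary outcomes. Response duration is not among them.

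**The concern.** A Kaplan-Meier curve cannot be drawn until someone decides what happens to a responder who dies with no progression on record. The only stated end of response is documented recurrence or progression. Followed as written, that patient fails in the PFS curve and does not fail in the response-duration curve, and the date at which follow-up stops is left to the analyst. The choice would then be made after the data are known.

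The situation is plausible here. Scans are eight weeks apart, the background section gives a median survival of 3 to 4 months from diagnosis, and the plan itself foresees patients leaving treatment with clinical decline but no objective progression. With no control arm, a response-duration curve is read at face value, so leaving these deaths out would on balance make responses look more durable than they were.

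**Working it through.** **The plan's own figure.** The documents give no number for response duration. The only related figure is the two-stage design in 12.6.2 (0/9, then at least 3/17; 5% against 30%). The probability of rejecting is the sum over x = 1 to 9 of b(x; 9, p) × P(Bin(8, p) ≥ 3 − x). This gives 0.0466 at p = 0.05 and 0.9045 at p = 0.30, so the stated 0.05 and 0.9 reproduce. Response duration does not enter this calculation. Expected responders among 17 are 17 × 0.30 = 5.1 under the alternative and 17 × 0.05 = 0.85 under the null.

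**Inputs from the plan.** Scan interval T = 2 × 28 = 56 days = 56/30.4375 = 1.84 months. Five responders, rounding 5.1.

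**Assumed inputs, not in the documents.** Median time from response to true progression is 3 months. Median survival after progression, m, is 2, 3.5 or 6 months; the background figure counts from diagnosis and cannot be used directly. Times are exponential. Physical examination documents either none or half of progressions at once. Deaths before any progression are not modelled.

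**Step 1: how often death precedes documentation.** With progression uniform within a scan interval and λ = ln 2 / m, the chance of dying before the next scan is f = 1 − (1 − e^(−λT))/(λT). For m = 3.5, λT = 0.198 × 1.84 = 0.364 and f = 1 − 0.305/0.364 = 0.162. If examination catches half at once, f is halved.

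**Step 2: effect on the reported median.** Each simulated trial (8,000 to 20,000 per scenario) was analysed with death as an event and under the literal rule. Because the plan gives no censoring date, the literal rule was run with censoring at death and with censoring at the last scan.

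| m (months) | f: no exam / half by exam | Censor at death, median longer: no exam / half by exam | Censor at last scan, half by exam: longer / shorter |
|---|---|---|---|
| 2 | 0.261 / 0.130 | 35% / 25% | 17% / 2.3% |
| 3.5 | 0.162 / 0.081 | 22% / 16% | 10% / 1.3% |
| 6 | 0.099 / 0.050 | 13% / 10% | 6% / 0.9% |

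With censoring at death the median was never shorter. With no detection by examination the two censoring dates give the same result. When the median did change under censoring at death, it was typically by one scan interval, 1.84 months (2.2 months at m = 2 with no detection by examination). Across trials the typical median stayed at 3.7 months, the second scan after response, under both rules, though only narrowly at m = 2 with no detection by examination.

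**Step 3: effect on the curve.** With censoring at death and m = 3.5, the share still in response at 6 months goes from 0.277 to 0.335 with no detection by examination (+6 points), and from 0.265 to 0.295 with half by examination (+3). The extremes over m are +10 points (0.277 to 0.377) and +2 (0.264 to 0.282).

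**Step 4: scale.** With 5 responders and a true median of 3.0 months under constant hazards, 95% of sample medians lie between 0.7 and 8.3 months. Sampling error is much larger than this bias.

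**Step 5: PFS wording.** With median OS 3.5 months and follow-up to month 36, about 0.05 to 0.2 of 17 patients are affected, depending on the assumed rate of stopping scans, and median PFS moves by at most about 0.04 months on average.

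**The case against.** The strongest reply is that the plan does not say deaths are censored. It is silent, and an analyst could sensibly carry over the PFS rule from the same section, in which case nothing goes wrong. That is fair as to what might happen, but it does not supply a rule: 10.1.3 does state an end of response, and death is not in it. The plan also asks for every effort to document progression after treatment stops and accepts examination findings. These reduce the number of undocumented cases but do not remove them.

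Three stronger readings are tempting and are not supported.

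- A reader might infer that any error must lengthen response. That requires censoring at the death date, which the plan does not specify. Suppose patient A is last scanned at month 2 and dies at month 4, B progresses at 3 and C at 10. With death as an event the median is 4; with A censored at month 2 it is 3. The net direction is upward, but not in every trial.
- A reader might infer that the median is inflated by 11% to 25%. That is 1/(1 − f) at f = 10% and 20% under continuous observation with constant hazards. On the plan's 8-week scans the typical median does not move.
- A reader might infer that the PFS censoring wording biases PFS. Death is already a PFS event, and the wording can be read harmlessly as the last progression-free assessment. A visible shift needs survival far beyond the plan's figures: an assumed OS median of 9 months with frequent loss to scans leaves 2.1 of 17 patients censored and moves the median by about 1.1 months.

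**Conclusion.** The gap is real and minor. Section 10.1.3 states an end of response that omits death, 12.5.2 puts it into a Kaplan-Meier analysis without a death or censoring rule, and no other section supplies one. On balance the literal rule overstates response duration: the reported median is longer in about 6% to 35% of trials and shorter in 0% to 2%, with no change in the typical median. The range reflects the open censoring date, detection by examination and assumed survival after progression. All of these figures rest on the assumed inputs listed in the working.

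Response duration is an additional descriptive estimate in perhaps five patients, and no decision rule uses it. The response rate, type I error, power, sample size and stage 1 rule stand as they are. The PFS wording merits tidying for consistency only.

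**What to change.** In 10.1.3 and 12.5.2, define response duration as ending at documented progression or death from any cause, whichever is first, and censor responders with neither at their last adequate tumour assessment. Give the definition of complete-response duration the same ending. In 12.5.2, use the last adequate tumour assessment as the PFS censoring date as well (day 1 if there is none), and keep the last-known-alive date for OS only.

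The cost is a few changes of wording. Scan dates are already collected and survival is already followed, so no new data are needed and the design is untouched. The downside is that reported response duration may be slightly shorter and that deaths unrelated to the cancer will end response, which is how the plan already treats PFS.
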